17.4. Date Imputation Guideline

This subsection gives guideline on imputation of complete or partial missing AEs start and/or stop dates.

17.4.1. Impute Missing Adverse Events/ Prior or Concomitant Medications

Incomplete Start Date:

Missing day and month

- If the year is the **same** as the year of the first dosing date (earliest of CC-122 or Nivolumab), then the day and month of the first doing date will be assigned to the missing fields.

- If the year is **prior to** the year of first dosing date (earliest of CC-122 or Nivolumab), then December 31 will be assigned to the missing fields.
- If the year is **after** the year of first dosing (earliest of CC-122 or Nivolumab), then January 1 will be assigned to the missing fields.

Missing day only

- If the month and year are the **same** as the year and month of first dosing date (earliest of CC-122 or Nivolumab), then the first dosing date will be assigned to the missing day.
- If either the year of the partial date is **before** the year of the first dosing date (earliest of CC-122 or Nivolumab) or the years of the partial date and the first dosing date are the same but the month of partial date is **before** the month of the first dosing date, then the last day of the month will be assigned to the missing day.
- If either the year of the partial date is **after** the year of the first dosing date (earliest of CC-122 or Nivolumab) or the years of the partial date and the first dose date are the same but the month of partial date is **after** the month of the first dosing date, then the first day of the month will be assigned to the missing day.
- If the stop date is not missing, and the imputed start date is after the stop date, the start date will be imputed by the stop date.

Missing day, month, and year

- No imputation is needed, the corresponding AE will be included as TEAE.

Incomplete Stop Date: If the imputed stop date is before the start date, then the imputed stop date will be equal to the start date.

Missing day and month

- If the year of the incomplete stop date is the **same** as the year of the last dosing date (latest of CC-122 or Nivolumab), then the day and month of the last dosing date will be assigned to the missing fields.
- If the year of the incomplete stop date is **prior to** the year of the last dosing date (latest of CC-122 or Nivolumab), or prior to the year of the first dosing date, then December 31 will be assigned to the missing fields.
- If the year of the incomplete stop date is **prior to** the year of the last dosing date (latest of CC-122 or Nivolumab), but is the same as the year of the first dosing date (earliest of CC-122 or Nivolumab), then the first dosing date will be assigned to the missing date.
- If the year of the incomplete stop date is **after** the year of the last dosing date (latest of CC-122 or Nivolumab), then January 1 will be assigned to the missing fields.

Missing day only

- If the month and year of the incomplete stop date are the **same** as the month and year of the last dosing date (latest of CC-122 or Nivolumab), then the day of the last dosing date will be assigned to the missing day.
- If either the year of the partial date is **not equal to** the year of the last dosing date (latest of CC-122 or Nivolumab) or the years of the partial date and the last dosing date are the same but the month of partial date is **not equal to** the month of the last dosing date, then the last day of the month will be assigned to the missing day.

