6. PROCEDURES

6.1. Screening Period

Screening evaluations will be performed for all subjects to determine study eligibility. These evaluations must be completed within 28 days prior to first dosing except as noted below and in [Table 3](#). All screening assessments must be performed prior to enrollment and subsequently treatment, however, these events may occur on the same calendar day as long as they are completed prior to enrollment.

Any questions regarding subject eligibility should be directed to the Celgene Medical Monitor or designee. Waivers to the protocol will not be granted during the conduct of this trial under any circumstances.

Unless otherwise specified, all assessments should be performed locally. Screening eligibility criteria laboratory values must demonstrate subject eligibility. Screening assessments may be repeated within the screening window if necessary, and the most recently obtained result should be used to demonstrate eligibility.

The following will be performed at screening as specified in the Table of Events ([Table 3](#)) after informed consent has been obtained:

- Review of inclusion/ exclusion criteria
- Commencement of pregnancy prevention counseling, per the PPRMP (Appendix G, Section [18.7](#))
- Demographics
- Prior cancer history (including specific information regarding diagnosis, staging, and histology)
- Prior cancer therapies: includes surgery, radiation, systemic, locoregional, or any other therapy (eg, hormonal) for the subject's cancer
- Medical history (all relevant medical conditions occurring < 28 days before screening should be included)
- Prior and concomitant medication evaluation (includes those taken \leq 28 days before the screening visit, except those taken for cancer which are recorded as part of prior cancer therapy)
- Prior and concomitant procedures (includes all procedures occurring \leq 28 days before the screening visit)
- Adverse event evaluation (begins when the subject signs the informed consent form [ICF])
- Physical examination (source documented only), height, weight
- Vital signs (including blood pressure, temperature and pulse)
- Eastern Cooperative Oncology Group Performance Status

- Ophthalmologic exam to include visual acuity, slit-lamp exam with fluorescein for the anterior chamber, iris, and with pupillary dilatation (if required and not contraindicated) to assess the vitreous

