All AEs will be recorded by the Investigator from the time the subject signs informed consent until 28 days after the last dose of CC-122 and until 90 days after the last dose of nivolumab and those SAEs made known to the investigator at any time thereafter that are suspected of being related to CC-122 or nivolumab. Adverse events and SAEs will be recorded on the AE page of the eCRF and in the subject's source documents. All SAEs must be reported to Celgene Drug Safety within 24 hours of the Investigator's knowledge of the event by facsimile, or other appropriate method, using the SAE Report Form, or approved equivalent form.

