11.1. Adverse Events

11.1.1. Summary of Adverse Events

AEs will be analyzed in terms of treatment-emergent adverse events (TEAEs) which are defined as any AEs that start between the date of first dose of study drug and 28 days after the last dose of CC-122 or 90 days after the last dose of Nivolumab, whichever is later. All AEs will be coded using the MedDRA[®] dictionary Version 21.0 or higher.

The incidence of TEAEs will be summarized by MedDRA SOC and PT. The intensity of AEs will be graded 1 to 5 according to the National Cancer Institute (NCI) Common Terminology Criteria for Adverse Events (NCI CTCAE) Version 4.03 or higher if possible. AEs that are not defined in the NCI CTCAE Version 4.03 or higher should be evaluated for severity/intensity according to Version 3.0. For all other AEs not described in the NCI CTCAE criteria, the intensity will be assessed by the investigator as mild (grade 1), moderate (grade 2), severe (grade 3), life-threatening (grade 4) or death (grade 5).

If a subject experiences the same AE more than once with a different grade, then the event with the highest grade will be tabulated in “by grade” tables. If a subject experiences multiple AEs under the PT (SOC), then the subject will be counted only once for that PT (SOC). In addition, AEs with a missing grade will be presented in the summary table as a grade category of “Missing” and will not be imputed.

A summary table of the subject incidence rate in each of the following categories will be provided. In addition, a table for each of the following categories will be produced where the incidence rate will be tabulated by SOC and PT and provided.

- TEAEs;
- TEAEs related to CC-122, Nivolumab and study drugs (CC-122 and/or Nivolumab);
- TEAEs of NCI CTCAE grade 3 or 4 by maximum NCI CTCAE grade;

- TEAEs related to CC-122, Nivolumab and study drugs (CC-122 and/or Nivolumab) with NCI CTCAE grade 3 or 4 by maximum NCI CTCAE grade;
- Grade 5 TEAEs with death outcome;
- Grade 5 TEAEs with death outcome related to CC-122, Nivolumab and study drugs (CC-122 and/or Nivolumab);
- Serious TEAEs;
- Serious TEAEs related to CC-122, Nivolumab and study drugs (CC-122 and/or Nivolumab);
- TEAEs leading to discontinuation of CC-122, Nivolumab and both study drugs (CC-122 and Nivolumab);
- TEAEs related to CC-122 leading to discontinuation of CC-122 and both study drugs (CC-122 and Nivolumab);

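### SAP 17.4.1 counts an adverse event with a wholly missing start date as treatment-emergent even when its recorded stop date is before first dose

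*SAP*

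**What the plan says.** **Definition.** SAP 11.1.1 limits treatment-emergent AEs (TEAEs) to "any AEs that start between the date of first dose of study drug and 28 days after the last dose of CC-122". For nivolumab the limit is 90 days, and the later of the two limits applies. SAP 4.2, Table 2 makes TEAE incidence and severity part of the Phase 1 primary endpoint.

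**Collection.** Protocol 10.1 states: "All AEs will be recorded by the Investigator from the time the subject signs informed consent". Protocol 3.2 allows screening of up to about 28 days, so pre-dose events are expected in the AE log.

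**Incomplete start dates.** SAP 17.2 sends incomplete AE log dates to Appendix 17.4. There, SAP 17.4.1 treats three patterns:

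- *Day and month missing.* If the year is that of first dose, "then the day and month of the first doing date will be assigned to the missing fields". No comparison with the stop date is listed.
- *Day missing.* In the month of first dose, the start becomes the first dosing date. In an earlier month, it becomes the last day of that month. The last bullet in this list is a check: "If the stop date is not missing, and the imputed start date is after the stop date, the start date will be imputed" from the stop date.
- *Day, month and year missing.* "No imputation is needed, the corresponding AE will be included as TEAE". The stop date is not mentioned.

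The only other consistency rule in the section concerns stop dates: "If the imputed stop date is before the start date, then the imputed stop date will be equal to the start date".

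**The concern.** Counting an AE as treatment-emergent is a sensible default when its timing is unknown. It is not sensible when a recorded stop date already shows that the event was over before first dose. An event cannot start after it has stopped, so such an AE fails the SAP 11.1.1 definition whatever its true start date. The rule for a wholly missing start overrides that definition.

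The SAP recognises the start-after-stop conflict, since it includes a check for it where only the day is missing. As laid out, the same screening event is classified correctly when its month is known and wrongly when less of the date is known.

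What is at stake is the accuracy of the TEAE tables by dose cohort. These matter because SAP 15 (item 2) says the study will not move into the expansion phase, and escalation cohorts are small. SAP 17.2 also has listings show log dates as recorded, so a listing could show a stop before first dose for an event that the table counts as treatment-emergent.

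**Working it through.** The documents give no figure on this point, so there is none to reproduce. The check applies the start-date rules as listed to events that are pre-dose by construction.

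**1. One event, three degrees of missingness.** First dose is 15 June 2017 and the recorded stop is 10 June 2017 (illustrative dates). A June start is used because a start in an earlier month is imputed before first dose even without the stop-date check.

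| Start as recorded | Start after SAP 17.4.1 | Counted as TEAE? |
|---|---|---|
| June 2017 | 15 June, then moved to 10 June by the check | No |
| 2017 | 15 June (5 days after the stop); no check listed | Yes |
| Wholly missing | None assigned | Yes |

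**2. All pre-dose events in a 28-day window.** Take every first-dose day in 2017 (an assumed, non-leap year), every start *a* = 1 to 28 days before first dose, and every complete stop date from the start to the day before first dose. There are *a* possible stops for each start.

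- Combinations: 365 × (1 + 2 + … + 28) = 365 × 406 = 148,190. None is truly treatment-emergent.
- *Day missing:* 0 of 148,190 become TEAEs. A start in an earlier month is imputed before first dose, and a start in the month of first dose is pulled back to the stop.
- *Day and month missing, check not applied:* an event escapes only if it started in the calendar year before first dose, because it is then set to 31 December. These number 1² + 2² + … + 28² = 28 × 29 × 57 / 6 = 7,714. The rest, 148,190 − 7,714 = 140,476, become TEAEs: 140,476 / 148,190 = 94.8%.
- *Day and month missing, check read as general:* 0%.
- *Wholly missing:* 148,190 of 148,190, or 100%, on either reading. There is no imputed start for the check to compare.

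These shares show how the rules act on such events. They are not an expected frequency, which the documents do not allow one to estimate.

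**3. Does another rule catch it?** The remaining consistency rule moves an imputed stop forward to the start, so it cannot remove a pre-dose event. SAP 17.2 adds no exclusion.

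**4. Size of one misclassified subject.** The most it can add to the incidence of one preferred term is 1/3 = 33.3 points in a cohort of 3, 1/6 = 16.7 points in a cohort of 6, and 1/20 = 5.0 points across about 20 Phase 1 subjects. These are maxima. SAP 11.1.1 counts a subject once per preferred term, so nothing is added if the subject also has a genuine TEAE of that term.

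**5. After the fix.** With one prior rule, that a complete stop date before first dose means not treatment-emergent, all three patterns give 0 of 148,190.

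**The case against.** **The trigger should be rare.** SAP 17.2 expects log dates to be complete unless the event is ongoing. Protocol 10.2.4 requires start and stop dates for every AE, and Protocol 14.2 and 15.1 provide edit checks, queries and source verification. The pattern needs an event recorded after consent with a known pre-dose stop but no start month or no start date. This stands, and it limits the practical effect.

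**The year-only branch rests on where a bullet sits.** The stop-date check is worded generally and names no missing-field pattern. The text was read from a PDF, so indentation may have been lost. This stands in part: the layout favours the narrow reading, but the general reading would cure that branch. It does not touch the wholly missing case.

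**The error is conservative and the analyses are descriptive.** Both are true. Over-counting is the cautious direction for safety, but it still departs from the SAP's own definition and can distort comparisons between dose levels.

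**Stronger inferences that the documents do not support:**

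- *That escalation or dose-limiting toxicity counts are affected.* Protocol 7.6 and 7.8 base escalation on toxicities within the Cycle 1 window, reviewed by the Safety Review Committee, not on imputed TEAE tables.
- *That a wholly missing start is placed on the first dosing day and so in Cycle 1 onset tables.* No date is assigned in that case. Such placement could arise only in the year-only branch.
- *That passing the 10% cut for common TEAEs is a special consequence.* Any single event in a cohort of 6 or fewer exceeds 10%, and the SAP does not say that the cut is applied by cohort.
- *That medication summaries are wrong too.* The section title mentions prior and concomitant medications, but SAP 17.4 describes the guideline as covering AE dates and the medication classification text is not visible. This cannot be assessed.

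**Conclusion.** The point holds for a wholly missing start date on any reading of SAP 17.4.1: a recorded stop before first dose is ignored, and the event is counted against the definition in SAP 11.1.1. It holds for a year-only start in the year of first dose if the stop-date check applies only where it is listed.

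The effect is an over-count of TEAEs and is probably small in practice. Per affected subject it is bounded by 16.7 points in a cohort of 6 and 33.3 points in a cohort of 3, for one preferred term. The conclusion assumes that at least one AE has this date pattern, which cannot be known from the documents. Correction is worthwhile because the endpoint is primary and the change is simple.

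**What to change.** Put one step ahead of the existing start-date rules in SAP 17.4.1, for every incomplete or missing AE start date:

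> First compare the stop date, as recorded and before any stop-date imputation, with the first dose date. If a complete stop date, or a partial stop date that is unambiguous, is before first dose, the AE is not treatment-emergent and any imputed start is no later than the stop. Otherwise apply the rules below.

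The existing rules then stay, including the default to TEAE for a wholly missing start when the stop date is missing, ongoing, not clearly before first dose, or on or after it. The comparison must use the stop date as recorded because stop-date imputation can move an imputed stop forward to the start and hide the conflict. A stop recorded only as May 2017, with first dose on 15 June 2017, is an unambiguous partial date. A stop recorded only as 2017 is not.

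The cost is a few sentences in the SAP and a small programming change. No new data are needed.

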17.5. Laboratory Data Handling Rules

The following data handling rules for laboratory parameters are for data analysis purpose (tables and figures). All original data will be presented as is in the data listings.

Table 11: Data Handling Conventions for Laboratory Parameters

Case	Convention	Example Data
values recorded as "<xx"	Set the numerical value to one tenth less in the next digit/decimal point	Immunoglobulin M (Serum) recorded as "<0.20" (g/l), set the numerical value to 0.199
values recorded as ">xx"	Set the numerical value to one tenth more in the next digit/decimal point	Creatinine clearance recorded as "> 60" (ml/min), set the numerical value to 60.1

17.6. PK Data Handling

Values Below the Limit of Quantification or Missing

Pre-dose concentrations that are below the limit of quantification (BLQ) or missing will be assigned a numerical value of zero. A BLQ value that occurs between pre-dose and the first quantifiable concentration point will be assigned a numerical value of zero. A BLQ value that occurs between quantifiable concentration points will be treated as missing. If BLQ values occur at the end of the collection interval, they will be assigned a numerical value of zero, unless otherwise warranted by the concentration-time profile. A concentration of zero occurring after quantifiable concentrations will be considered as missing for the calculation of PK parameters. Concentrations assigned a value of missing will be omitted from the calculation of descriptive statistics. A concentration value of zero will be included for the computation of arithmetic mean, and a post-dosing zero concentration will be substituted with a 50% value of the low limit of quantification (LLOQ), for the computation of geometric mean. If 50% or more of the values are BLQ at one timepoint, the arithmetic mean, median, and geometric mean will be reported as BLQ, and other descriptive statistics will not be calculated.

[REDACTED]

[REDACTED]	[REDACTED]	[REDACTED]
[REDACTED]	[REDACTED]	[REDACTED]

[REDACTED]

[REDACTED]

[figure not shown]
[REDACTED]	[REDACTED]	[REDACTED]
[REDACTED]	[REDACTED]	[REDACTED]
[REDACTED]	[REDACTED]	[REDACTED]

17.8. Study Procedures

Table 14: Table of Events

	Screening Period		Treatment Period											Follow-up Period	Follow-up Period	
	Screening ^a	Cycle 1				Cycle 2					Subsequent Cycles		EOT			
Day ^b	-28 to -1	1 ^c	8	15	22	1	8	15	18	22	1	15		28 day follow-up	90 days follow-up	Disease Progression/ Survival/ Pregnancy
STUDY ENTRY																
Informed consent	X															
Pregnancy prevention counseling	Pregnancy risk counseling and education prior to dispensing of IP															
Demographics	X															
Prior cancer history	X															
Prior/post cancer therapies	X													At the same schedule as survival visits		
Complete medical history	X															
	X															
	X															
Inclusion/exclusion criteria	X															
SAFETY ASSESSMENTS																
Adverse event collection	Continuous starting after informed consent signature, until 28 days after last dose of CC-122 and 90 days after the last dose of Nivolumab or at any time afterwards if the PI feels the event is related to any IP															
Physical examination (source documented only)	X	X				X					X		X			

	Screening Period	Treatment Period												Follow-up Period	Follow-up Period	
	Screening ^a	Cycle 1				Cycle 2					Subsequent Cycles	EOT				
Day ^b	-28 to -1	1 ^c	8	15	22	1	8	15	18	22	1	15		28 day follow-up	90 days follow-up	Disease Progression/ Survival/ Pregnancy
Ophthalmologic exam	X	As clinically indicated														
Weight	X	X				X					X		X			
Height	X															
Vital signs	X	X ^b	X	X	X	X					X		X			
ECOG PS	X	X ^a				X					X		X			
CBC with differential	X (-14 to -1)	X ^a	X	X	X	X	X	X	X	X	X	X Cycles 3-6 only	X			
Coagulation: PT, INR, PTT	X (-14 to -1)	X ^a				X					X					
Troponin-T and BNP	X	X ^a	X	X	X	X					X		X			
Chemistry laboratory (fasting, routine)	X (-14 to -1)	X ^a	X	X	X	X	X	X		X	X		X			
Amylase, lipase, T3, CK, TSH, fT4, immunoglobulins (IgG, IgM and IgA only) and T cell subsets (CD4+ and CD8+)	X	X ^a		X		X		X			X		X			
HBV and HCV serologies (HBsAg, HBeAg, HBsAb, HBeAb, HBcAb, HCVAb)	X															
HCV viral load	X															
HBV viral load	X	If HBsAg and/or HBcAb positive at screening, on day 1 of each cycle and at EOT														

	Screening Period	Treatment Period											Follow-up Period	Follow-up Period			
	Screening ^a	Cycle 1				Cycle 2					Subsequent Cycles	EOT		28 day follow-up	90 days follow-up	Disease Progression/Survival/Pregnancy	
Day ^b	-28 to -1	1 ^c	8	15	22	1	8	15	18	22	1	15					
Urinalysis	X (-14 to -1)					X					X						
Triplicate 12-lead electrocardiogram	X	X	X	X	X	X					X		X				
LVEF	X										X every 3 cycles		X				
Serum β-hCG (in FCBP)	X (-14 to -1)	As PPRMP indicated – to be updated according to PPRMP															
Urine β-hCG (females of childbearing potential [FCBP] only)	X ^d (-14 to -1)	As PPRMP indicated – to be updated according to PPRMP															
EFFICACY ASSESSMENTS																	
PK samples (Intensive or sparse, multiple time points)		X		X													
	■	■	■	■	■	■		■	■		■						
	■																

	Screening Period	Treatment Period											Follow-up Period	Follow-up Period			
	Screening ^a	Cycle 1				Cycle 2					Subsequent Cycles			EOT	28 day follow-up	90 days follow-up	Disease Progression/Survival/Pregnancy
Day ^b	-28 to -1	1 ^c	8	15	22	1	8	15	18	22	1	15					
Fresh paired tumor biopsy	X ^f								D18 (+/- 7 days, preferably after 3 continuous days of CC-122 administration) ^g								
Tumor evaluation (CT or MRI)	X (-28 to -1)	RECIST 1.1 and irRECIST algorithm: Every 8 weeks (±7 days) for the first 10 months, then every 12 weeks (±7 days), until death, lost to follow up, progression or start of new anticancer therapy. See Sections 6.5.1 and 6.5.2 in the protocol															
Alpha-fetoprotein	X	X				X					X		X				
INVESTIGATIONAL PRODUCT																	
Administer CC-122		5/7 days continuously															
Administer Nivolumab		Q2W															
CC-122 accountability		X	X	X	X	X	X	X		X	X	X	X				
Nivolumab accountability		Q2W											X ^h			X ^h	
FOLLOW-UP																	
Survival follow-up																	Every 3 months (+/- 7 days)

Abbreviations: β-hCG = beta human chorionic gonadotropin; BNP = brain natriuretic peptide; CBC = complete blood count; CK = creatine kinase; CT = computed tomography; ECOG PS = Eastern Cooperative Oncology Group Performance Status; EOT = End of Treatment; FCBP = females of child bearing potential; FFPE = formalin-fixed, paraffin embedded; fT4 = free T4; HBV = hepatitis B virus; HBsAg = hepatitis B surface antigen; HBeAg = hepatitis B e antigen; HBsAb= hepatitis B surface antibody; HBeAb = hepatitis B e antibody; HBcAb = hepatitis B core antibody; HCVAb = HCV antibody; HCV = hepatitis C virus; IG = immunoglobulin; INR = international normalized ratio;

LVEF = left ventricular ejection fraction; MRI = magnetic resonance imaging;; PI = Primary Investigator; PK = pharmacokinetic; PPRMP = Pregnancy Prevention Risk Management Plan; PT = prothrombin time; PTT = partial thromboplastin time; RECIST 1.1 = Response Evaluation Criteria in Solid Tumors Version 1.1; TSH = thyroid stimulating hormone.

- ^a All screening assessments must be performed prior to enrollment and subsequently treatment, however, these events may occur on the same calendar day as they are completed prior to enrollment.
- ^b An administrative window of ± 3 days is permitted for all cycles except Cycle 1 Day 1 (CID1).
- ^c CID1 assessment may be omitted if screening assessment performed within 72 hours of first dose with the exception of the pregnancy test, see footnote d.
- ^d As per PPRMP, FCBP must have two negative pregnancy tests (sensitivity of at least 25 mIU/mL) prior to starting CC-122. The first pregnancy test must be performed within 10-14 days prior to the start of CC-122 and the second pregnancy test must be performed within 24 hours prior to the start of CC-122. The subject may not receive CC-122 until the study doctor has verified that the results of these pregnancy tests are negative.
- ^e [REDACTED]
- ^f Archival tumor tissue will be required only if fresh tissue is not evaluable at screening. See Sections 6.8.1 and 6.8.2 in the protocol.
- ^g Sample may be collected on Day 18 ± 7 days of Cycle 2. The sample must be collected at 3 to 6 (± 1) hours postdose. Due to the intermittent schedule of CC-122 administration, the sample should preferably be collected after at least 3 continuous days of administration.
- ^h After discontinuation of Nivolumab, females of childbearing potential must use effective contraception for at least 5 months.

